7.3.3 Safety analyses

The occurrence of dose limiting toxicity (DLT) as well as the incidence and intensity of adverse events graded according to CTCAE, laboratory parameters, vital signs and duration of neutropenia will be evaluated.

All patients of the full analysis set (both phase I and phase II) will be included in the safety analyses.

Two analyses will be performed. The first analysis of safety will be performed for the first part of the trial (determination of the MTD, first cycle only, treatment regime=initial dose at the start of the treatment, full analysis set (phase I only)). This descriptive analysis will evaluate the MTD for each treatment schedule. The second analysis will be performed with

respect to all cycles and will act as a support for the determination of the MTD (full analysis set (both phase I and phase II)).

Incidence and intensity of adverse events

The severity, and timing of adverse events will indicate how well the treatment regimen is tolerated. Toxicities will be evaluated using the CTCAE grading scheme.

The overall incidence and intensity of adverse events, as well as relatedness of adverse events to treatment with BI 6727 monotherapy and in combination with cytarabine, respectively, will be reported for all treatment schedules.

Serious adverse events will be tabulated. In addition, events leading to dose reduction or treatment discontinuation will be examined, but may not be reported as individual tables, depending upon the extent of overlap with the occurrence of DLT.

Descriptive statistics will be used to describe changes in laboratory tests over time. In addition, all abnormalities of potential clinical relevance will be reported.

Events that started within the period starting with first administration of the trial drug and ending six weeks after the first treatment administration in the last treatment cycle will be considered as having occurred during treatment. In general, later events will be attributed to the post-study period and will be presented separately. However, post-study events will be examined to determine whether they need to be combined with on-treatment events in an additional table.

ECG measurements

Prolongation of QT/QTc times will be analysed descriptively and exploratory based on the ECG measurements described in [Section 5.2.7](#). Further details of the analysis of ECG data will be specified in the statistical analysis plan.

7.3.4 Interim analyses

Early analyses of response to therapy will be performed before completion of recruitment in order to support internal strategic decision making and planning for future clinical trials. In order to avoid bias of these early efficacy analyses on trial conduct, the results will not be distributed to trial sites before database lock for the CTR (see [section 6.2.3.3](#)). The analyses will be performed when approximately 50% of planned patients in the phase II part of the trial have either stopped treatment or completed at least two treatment cycles. Details of the early analyses of response to therapy will be specified in the interim trial statistical analysis plan. The early efficacy analyses will be documented and archived. If considered necessary for internal strategic decision making the early efficacy analysis may be repeated once when approximately 70% of planned patients in the phase II part of the trial have either stopped treatment or completed at least two treatment cycles.

After all patients of treatment schedule A that are contained in the full analysis set (phase I) have either completed at least one course of BI 6727 in combination with cytarabine or

dropped out of the study, a safety analysis will be performed. For this purpose a database snapshot will be performed. The safety analysis will summarize results regarding safety of the patients in the phase I part and will contain the determination of the MTD as well as a recommendation for the dose of BI 6727 to be used in the phase II part of the study. The selection of the recommended dose for the phase II part will consider overall safety observed during all treatment cycles. No efficacy comparisons will be performed in this phase I safety analysis. Detailed specifications of the phase I safety analysis are provided in the TSAP. The phase I safety analysis will be documented and archived.

For other safety purposes database snapshots can be performed as deemed appropriate.

7.3.5 Pharmacokinetic methods

7.3.5.1 Pharmacokinetic analyses

The following basic pharmacokinetic parameters will be calculated in cycle 1 for BI 6727 in plasma for schedules A and B on visits 1 and 4 and for cytarabine in plasma for schedule C on visits 1 and 3 (refer to [section 10.1](#)).

Additional parameters may be determined if deemed necessary:

- C_{\max} (maximum measured concentration of BI 6727 or cytarabine in plasma)
- t_{\max} (time from dosing to maximum measured concentration)
- $AUC_{0-\infty}$ (area under the concentration-time curve of BI 6727 or cytarabine in plasma over the time interval from 0 extrapolated to infinity)
- AUC_{0-24} (area under the concentration-time curve of BI 6727 or cytarabine in plasma over the time interval from 0 to 24)
- $t_{1/2}$ (terminal half-life of BI 6727 or cytarabine in plasma)
- MRT (mean residence time of BI 6727 or cytarabine in the body after intravenous or subcutaneous administration, respectively)
- CL (total clearance of BI 6727 in plasma after intravascular administration)
- CL/F (total clearance of cytarabine in plasma after subcutaneous administration)
- V_z (apparent volume of distribution during the terminal phase λ_z following a intravascular dose of BI 6727)
- V_z/F (apparent volume of distribution during the terminal phase λ_z following a subcutaneous dose of cytarabine)
- V_{ss} (apparent volume of distribution at steady state following intravascular administration of BI 6727)

Pharmacokinetic parameters after first and second administration will be compared in a descriptive manner.

The pharmacokinetic parameters C_{max} , $AUC_{0-\infty}$ and AUC_{0-24} will be explored with respect to dose proportionality (if more than 2 doses are investigated).

All evaluable patients will be included in the pharmacokinetic analysis. A patient is considered to be not evaluable if the subject has an important protocol violation relevant to the evaluation of pharmacokinetics or has insufficient data. Patients who are considered as not evaluable will be listed with their individual plasma concentrations and individual pharmacokinetic parameters, however, will not be included in descriptive statistics for plasma concentrations, pharmacokinetic parameter evaluation or other statistical assessment.

The following descriptive statistics will be calculated for BI 6727 and cytarabine concentrations as well as for all pharmacokinetic parameters: N, arithmetic mean, standard deviation, minimum, median, maximum, arithmetic coefficient of variation, geometric mean, geometric coefficient of variation. Descriptive statistics of concentrations at specific time points will be calculated only when at least 2/3 of the individuals have concentrations within the validated concentration range. The overall sample size to decide whether the “2/3 rule” is fulfilled will be based on the total number of samples intended to be drawn for that time point. Descriptive statistics of parameters will be calculated only when at least 2/3 of the individuals have parameters. The overall sample size to decide whether the “2/3 rule” is fulfilled will be based on the total number of patients included in the analysis of the parameter.

Pharmacokinetic parameters of cytarabine dosed along with BI 6727 will be compared in a descriptive manner to those of cytarabine dosed alone to assess the effect of BI 6727 on cytarabine pharmacokinetics. Similarly, pharmacokinetic parameters of BI 6727 obtained in treatment schedule A will be compared to the parameters obtained in treatment schedule B to assess the effect of cytarabine on BI 6727 pharmacokinetics.

Refer to [Appendix 10.1](#) for details concerning derivation of pharmacokinetic parameters.

7.3.5.2 Pharmacogenetic analyses

Pharmacogenetic analyses will be carried out using an explorative approach on anonymised samples, if they are deemed helpful to interpret the pharmacokinetics, efficacy, and safety data of BI 6727.

7.4 HANDLING OF MISSING DATA

Every effort will be made to obtain complete information on all AEs, with particular emphasis on potential dose limiting toxicities.

If not stated otherwise, missing data will not be imputed and remain missing. Potential outliers will be reported and analysed as observed.

The occurrence of missing data should be minimised by follow-up of patients for both disease progression and mortality after end of trial for an individual patient. Both response and progression status for patients who are lost to follow-up or who die before progression has been documented, will be assessed at the end of the trial.

Laboratory value: Missing baseline laboratory values will be imputed by respective values from the screening visit.

Pharmacokinetic parameters

Concentration data identified with NOS (no sample), NOR (no valid result), NOA (not analyzed), BLQ (below the limit of quantification), and NOP (no peak detectable) will be ignored and not replaced by zero at any time point (applies also to the lag phase). Descriptive statistics of concentrations at specific time points will be calculated only when at least 2/3 of the individuals have concentrations within the validated concentration range. The overall sample size to decide whether the “2/3 rule” is fulfilled will be based on the total number of samples intended to be drawn for that time point (i.e. BLQ, NOR, NOS, NOA, NOP are included).

In the noncompartmental analysis, concentration data identified with NOS, NOR, and NOA will not be considered. BLQ and NOP values in the lag phase will be set to zero. The lag phase is defined as the period between time zero and the first time point with a concentration above the quantification limit. All other BLQ/NOP values of the profile will be ignored.

If the predose concentration is less than or equal to 5 percent of C_{max} value in that subject, the subject's data without any adjustments can be included in all pharmacokinetic measurements and calculations (i.e. the predose value will not be changed to zero). If the predose value is greater than 5 percent of C_{max} , the subject should be dropped from all statistical evaluations. The individual pharmacokinetic parameters can be calculated and listed separately.

Every effort will be made to include all concentration data in an analysis. If not possible, a case to case decision is required whether the value should only be excluded from half-life estimation or the complete analysis.

- If a concentration is only excluded from half-life determination, it will be used for all other calculations (e.g. descriptive statistics) and for graphical presentation
- If a concentration value is excluded from all calculations, it will not be presented graphically or used for the calculation of descriptive statistics and parameter determination. However, the excluded concentration itself will be listed in the tables in section 15 of the clinical trial report associated with an appropriate flag.

Descriptive statistics of parameters are calculated only when at least 2/3 of the individual parameter estimates of a certain parameter are available. If the actual sampling time will not be recorded or will be missing for a certain time point, the planned time will generally be used for this time point instead. Pharmacokinetic parameters which cannot be determined will be identified by "not calculated" (NC).

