If the predose concentration before the first dose is less than or equal to 5% of C_{max} value in that subject, the subject's data without any adjustments can be included in all pharmacokinetic measurements and calculations (i.e., the predose value will not be changed to zero). If the predose value is greater than 5% of C_{max} , the subject should be dropped from all statistical evaluations. The individual pharmacokinetic parameters can be calculated and listed separately.

Every effort will be made to include all concentration data in an analysis. If not possible, a

case to case-to-case decision is required whether the value should only be excluded from half-life estimation or the complete analysis.

- If a concentration is only excluded from half-life determination, it will be used for all other calculations (e.g., descriptive statistics) and for graphical presentation.
- If a concentration value is excluded from all calculations, it will not be presented graphically or used for the calculation of descriptive statistics and parameter determination. . However, the excluded concentration itself will be listed in the clinical trial report associated with an appropriate flag.

Descriptive statistics of parameters are calculated only when at least 2/3 of the individual parameter estimates of a certain parameter are available. If the actual sampling time will not be recorded or will be missing for a certain time point, the planned time will generally be used for this time point instead. Pharmacokinetic parameters which cannot be determined will be identified by "not calculated" (NC).

C_{max} and t_{max}: Individual C_{max} and t_{max} values will be directly determined from the plasma concentration time profiles of each subject. If the same C_{max} concentration occurs at different time points, t_{max} is assigned to the first occurrence of C_{max}.

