Estimation of λ_z: The apparent terminal rate constant λ_z will be estimated from a regression of ln(C) versus time over the terminal log-linear disposition portion of the concentration-time profiles. The log-linear profiles, which include the regression line through the terminal points, will be checked via visual inspection, and it will be determined whether the regression appropriately represents the terminal slope. A minimum of three points will be used in the determination of λ_z. If the last concentration-time point increases, this time point may be included if the t_{1/2} estimate is reasonable. If λ_z is not determinable then consequently only parameters not requiring λ_z will be reported. In addition, the lower (t_{λ_z,start}) and upper (t_{λ_z,end}) limit on time for values to be included in the calculation of λ_z will be listed.

t_{1/2}: The terminal half-life will be calculated from the terminal rate constant using the equation

$$t_{1/2} = \frac{\ln 2}{\lambda_z}$$

AUC: The area under the curve will be calculated using the linear up/log down algorithm. If an analyte concentration is equal to or higher than the preceding concentration, the linear trapezoidal method will be used. If the analyte concentration is smaller than the preceding concentration, the logarithmic method will be used.

Linear trapezoidal rule (t₂ > t₁ and C_{t2} ≥ C_{t1}):

The area of the trapezoid between the two data points (t₁, C_{t1}) and (t₂, C_{t2}) will be computed by:

$$AUC_{t1-t2} = 0.5 \times (t_2 - t_1) \times (C_{t1} + C_{t2})$$

Logarithmic trapezoid rule (t₂ > t₁ and C_{t2} < C_{t1}):

The area of the trapezoid between the two data points (t₁, C_{t1}) and (t₂, C_{t2}) will be computed by:

$$AUC_{t1-t2} = \frac{(t_2 - t_1) \times (C_{t2} - C_{t1})}{\ln(C_{t2}/C_{t1})}$$

AUC_{0-∞}: The area under the plasma concentration-time curve over the time interval from 0 extrapolated to infinity will be calculated according to the following equation

$$AUC_{0-\infty} = AUC_{0-tz} + \frac{C'_{tz}}{\lambda_z}$$

where C'_{tz} is the concentration predicted by the regression line for the time t_z (time of last measurable concentration of the analyte in plasma). The area under the concentration-time curve over the time interval from 0 to the last quantifiable plasma concentration (AUC_{0-tz}) will be calculated by the linear up/log down method as described above.

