%AUC_{tz-∞}: The percentage of the AUC_{0-∞} will be obtained by extrapolation according to the following equation:

$$\% AUC_{tz-\infty} = \frac{AUC_{0-\infty} - AUC_{0-tz}}{AUC_{0-\infty}} \times 100$$

MRT: The mean residence time after intravenous bolus injection will be calculated as follows:

$$MRT = \frac{AUMC_{0-\infty}}{AUC_{0-\infty}}$$

In order to compare the mean residence time after intravenous bolus administration (MRT) and intravenous infusion (MRT_{inf}), the following equation will be used in addition, where T represents the infusion time.

$$MRT = MRT_{inf} - (T \times 0.5)$$

The area under the first moment curve from time 0 to infinity ($AUMC_{0-\infty}$) is calculated according to:

$$AUMC_{0-\infty} = AUMC_{0-tz} + \frac{C_{tz} \times tz}{\lambda_z} + \frac{C_{tz}}{\lambda_z^2}$$

CL: The total clearance after intravenous administration will be determined according to the following equation:

$$CL = \frac{Dose}{AUC_{0-\infty}}$$

(F = absolute bioavailability factor)

V_z: The apparent volume of distribution during the terminal phase after intravascular administration will be determined according to the following equation:

$$V_z = \frac{CL}{\lambda_z}$$

V_{ss}: After single intravenous bolus administration or intravenous infusion when the mean residence time has been adapted as described above, the distribution volume in the steady state will be calculated according:

$$V_{ss} = CL_{ss} \times MRT_{ss}$$

gMean, gCV: The geometric mean (gMean) and coefficient of variation, gCV (given in %), will be calculated by the formulae:

$$gMean = \exp \left[\frac{1}{n} \sum_{i=1}^n \ln(x_i) \right] = \exp \left[\overline{\ln(x_i)} \right]$$

$$gCV(\%) = 100 \cdot \sqrt{\exp[\text{Var}(\ln(x_i))] - 1}$$

where

$$\text{Var}(\ln(x_i)) = \frac{1}{n-1} \sum_{i=1}^n \left[\ln(x_i) - \overline{\ln(x_i)} \right]^2.$$

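### Section 7.4 and Appendix 10.1.1 give the 5% pre-dose exclusion different scope, and neither corrects BI 6727 AUC0-∞ and clearance after the second dose for drug left from the first

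*Protocol*

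**What the plan says.** Protocol section 7.3.5.1 plans non-compartmental parameters "for BI 6727 in plasma for schedules A and B on visits 1 and 4". The list includes AUC0-∞, CL, Vz and Vss. It adds: "Pharmacokinetic parameters after first and second administration will be compared in a descriptive manner".

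Two sections then deal with a measurable pre-dose concentration:

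- Section 7.4 keeps the patient unadjusted "If the predose concentration is less than or equal to 5 percent of" Cmax. Otherwise, "If the predose value is greater than 5 percent of" Cmax, "the subject should be dropped from all statistical evaluations"; the individual parameters may still be listed. No dose is named, and it is not said which Cmax is meant.
- Appendix 10.1.1 repeats the rule but opens with "If the predose concentration before the first dose is less than or equal to 5% of" Cmax. It has no rule for the day-15 pre-dose sample.

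The formulas in Appendix 10.1.1 do not distinguish the doses. The area "extrapolated to infinity will be calculated according to the following equation": the observed area plus the predicted last concentration over λz. "The total clearance after intravenous administration will be determined according to the following equation": dose over AUC0-∞. There is no residual term, and no area over the dosing interval is listed.

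SAP sections 6.6 and 7.7.5 refer missing PK data, outliers and standard PK parameters to internal company documents and do not settle the difference.

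**The concern.** The day-15 pre-dose sample (335:55) may contain drug from day 1. The two texts treat a patient above 5% of Cmax at that sample in opposite ways. Under 7.4 the whole subject leaves the statistics, and the reason for leaving is slow elimination, one of the things being estimated. Under the appendix the patient stays.

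For every patient who stays, under either text, dose-2 AUC0-∞ includes the remainder of dose 1. Clearance would then appear to fall between day 1 and day 15 even if it were constant, and a reader could take this for time-dependent kinetics.

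Exclusion could also matter for the comparison of schedules A and B. If cytarabine slowed BI 6727 elimination, 7.4 would tend to remove the patients who show it.

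**Working it through.** The plan states no figure to reproduce. As a check that the sampling tables were read correctly, the blood volumes agree with section 5.5.1.1: schedule A 18 × 3 + 7 × 5 = 89 mL (stated as around 90), B 18 × 3 = 54 mL, C 7 × 5 = 35 mL.

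**Inputs from the documents.** Dosing interval 336 h and pre-dose sample at 335:55. After dose 2, samples run to 340:00 (4–6 h after dose) and then once at 648:00, which is 648 − 336 = 312 h after dose 2. λz needs at least three points.

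**Assumed.** Half-life and the share f of peak concentration that belongs to the terminal phase. Kinetics are linear. Where there is a fast phase, its half-life is 2 h.

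**Step 1: a patient above 5% of Cmax at 335:55.**

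| | Section 7.4, literal | Appendix 10.1.1 |
|---|---|---|
| Dose-1 parameters | excluded, may be listed | kept |
| Dose-2 parameters | excluded, may be listed | kept, uncorrected |

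**Step 2: carry-over in dose-2 AUC0-∞.** With the peak scaled to 1 and fast rate constant α, single-dose AUC0-∞ = (1 − f)/α + f/λz. The dose-1 tail beyond 336 h is f × 2^(−336/t½)/λz. Inflation r is tail divided by AUC0-∞, and CL2/CL1 = 1/(1 + r). Example for f = 0.05, t½ = 100 h: f/λz = 7.21, (1 − f)/α = 2.74, AUC0-∞ = 9.95, tail = 7.21 × 0.0974 = 0.70, so r = 7.1%.

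| Assumed t½ (h) | f = 1 | f = 0.3 | f = 0.05 |
|---|---|---|---|
| 48 | 0.8% | 0.7% | 0.4% |
| 60 | 2.1% | 1.9% | 1.3% |
| 80 | 5.4% | 5.1% | 3.7% |
| 100 | 9.7% | 9.3% | 7.1% |
| 120 | 14.4% | 13.8% | 10.9% |
| 150 | 21.2% | 20.5% | 16.9% |

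CL2/CL1 is therefore 0.91–0.93 at 100 h and 0.87–0.90 at 120 h.

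**Step 3: who would be dropped under 7.4.** The trigger is f × 2^(−336/t½) > 0.05, that is t½ > 336/log2(f/0.05). Taking, for illustration, log-normal half-lives with median 120 h and log-SD 0.3:

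| f | Trigger t½ | Dropped |
|---|---|---|
| 0.3 | 130 h | about 39% |
| 0.2 | 168 h | 13% |
| 0.1 | 336 h | 0.03% |

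At f = 0.3 the geometric mean half-life of those kept falls from 120 to 99 h. With a single phase (f = 1) the trigger is about 78 h against dose-1 Cmax and 79 h against dose-2 Cmax.

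**Step 4: the 5% cut-off does not bound the AUC bias.** At f = 0.05 and 120 h the pre-dose value is 0.05 × 0.1436 = 0.7% of Cmax, so the patient is kept unadjusted, yet AUC0-∞ is 10.9% too high.

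**Step 5: the planned dose-2 sampling.** Two-phase profiles were run with a 1 h infusion, slow half-life 48–140 h, fast half-life 1 or 3 h and f from 0.02 to 0.2. They used the planned sampling times and λz forced from the last three points.

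- The dose-2/dose-1 ratio of AUC0-∞ came out at 1.2–3.8. True carry-over was at most 18.5%, so most of the larger ratios comes from the sampling gap.
- Dose-1 AUC0-∞ was 1–16% above its true value.
- The pre-dose value was at most 4.7% of dose-2 Cmax, so Cmax was raised by at most about 0.047/(1 − 0.047) = 4.9%.

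**The case against.** The strongest reply is that the texts can be reconciled. Section 7.3.5.1 sends the reader to Appendix 10.1 for derivation details, and the appendix is the more specific text. If it governs, nobody is dropped for day-15 carry-over. That is a reasonable reading, but nothing in the protocol says that the appendix prevails, and it leaves the uncorrected AUC0-∞ and CL untouched.

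Second, Appendix 10.1.1 reports only parameters not requiring λz when λz cannot be determined. With one sample after 4–6 h, dose-2 AUC0-∞ and CL may often go unreported. This stands in part, but it rests on visual inspection patient by patient rather than on a stated rule. It also means that subtracting the residual would not by itself make the dose-2 comparison sound.

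Third, a reader might infer that the A-versus-B comparison carries the same bias. It does not in general. Both schedules share dosing days and BI 6727 sampling times, so equal half-lives give equal inflation, which cancels in the ratio. At f = 0.3, 120 h against 100 h leaves 1.138/1.093, about 4%. Dose-1 data give a comparison free of carry-over, unless 7.4 exclusions differ between schedules.

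Fourth, the internal PK documents were not available, and a carry-over procedure there cannot be excluded. It would not remove the conflict inside the protocol.

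**Conclusion.** The difference in scope between the two sections is certain from the text. So is the absence of a residual correction in the protocol's formulas. Under linear kinetics the direction of the bias is known: dose-2 CL is too low. Its size depends on a half-life that the documents do not give. AUC0-∞ inflation is under 1% at 48 h or less, about 7–10% at 100 h and 11–14% at 120 h, and it changes only moderately with the terminal share.

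The exclusion effect is much less certain. A reader might infer that 7.4 will discard a large share of patients. The documents do not support any particular share: the illustration moves from 39% to almost none as f goes from 0.3 to 0.1.

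A reader might also infer that the two doses cannot be compared validly at all. That goes too far. Short half-lives make carry-over negligible. Cmax is little affected where there is a marked distribution phase, although with a single-phase decline it would rise about as much as AUC0-∞. Pre-dose concentration remains usable.

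PK is a secondary endpoint and the comparison is descriptive. The MTD rests on DLTs. This is a should-fix point, with medium confidence because of the missing half-life.

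**What to change.** 1. Limit the pre-dose rule in section 7.4 to the sample before the first dose, as in Appendix 10.1.1, so that no patient is excluded for day-15 or cycle-2 carry-over.
2. Report AUC0-∞, CL, Vz and Vss for BI 6727 from dose 1 only. Compare the doses on Cmax and pre-dose concentration, read together so that the residual contained in dose-2 Cmax is visible.
3. If dose-2 AUC0-∞ is reported at all, subtract C(335:55)/λz, with λz taken from that patient's dose-1 samples (24, 96, 216 and 336 h). State that the absence of samples between 4–6 h and 312 h after dose 2 still limits the result.

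The cost is a few sentences in the protocol or SAP. All the samples needed are already scheduled.
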